3.1.1 Inclusion Criteria

To be eligible for this study, patients must fulfill all of the following inclusion criteria:

1. The presence of metastatic pancreatic adenocarcinoma plus 1 of the following:
 - a. Histological diagnosis of pancreatic adenocarcinoma confirmed pathologically, OR
 - b. Pathologist-confirmed histological/cytological diagnosis of adenocarcinoma consistent with pancreas origin in conjunction with either:
 - i. The presence of a mass in the pancreas, OR
 - ii. A history of pancreatic adenocarcinoma.
2. Measurable disease per RECIST v.1.1.
3. Patient must have documented tumor progression during or following a gemcitabine-containing regimen for the treatment of metastatic disease. Diagnosis of progression (by computed tomography [CT] or magnetic resonance imaging [MRI] scan or clinical progression) must be within 28 days prior to Randomization.
4. Only 1 prior gemcitabine-containing therapy and no other prior therapies for metastatic disease.
5. Male or non-pregnant, non-lactating female, ≥ 18 years or age.
 - a. If a female patient is of child-bearing potential, as evidenced by menstrual periods, she must have a negative serum pregnancy test (beta-human chorionic gonadotropin [β -hCG]) documented prior to the first administration of study drugs.
 - b. If sexually active, the patient must agree to use contraception considered adequate and appropriate by the Investigator (see [Appendix H](#) for full list of acceptable methods) during the period of administration of study drugs. In addition, male and female patients must utilize contraception after the end of the treatment as recommended in the individual drugs comprising FOLFOX product's Summary of Product Characteristics or Prescribing Information provided in the Pharmacy Manual and the Clinical Trial Facilitation Group, provided in [Appendix H](#).

6. Provide signed written informed consent.
7. ECOG PS of 0–1.
8. Patient must have completed prior chemotherapy and any investigational therapy at least 2 weeks (washout period) prior to Randomization and recovered from toxicity to Grade 1 or baseline.
9. Willingness and ability to comply with study requirements.
10. Patient has adequate organ function by the following laboratory assessments at baseline (obtained ≤ 21 days prior to Randomization):

Hematologic

- Platelets $\geq 100 \times 10^9/L$
- Hemoglobin ≥ 9.0 g/dL
- Absolute Neutrophil Count (ANC) $\geq 1.5 \times 10^9/L$

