5.2 Dose Interruption, Reduction, and Dose Schedule Modifications

If a non-hematologic AE is attributed to only 1 drug (ie, AM0010, oxaliplatin, or 5-FU), the Investigator should determine if the drug will be continued based on the Investigator's assessment of risk-benefit per the guidelines outlined below. For example, neuropathy, is clearly related to oxaliplatin; therefore, 5-FU/LV as well as AM0010 would not be responsible for this AE.

Hematologic Toxicity Dose Schedule Adjustment Requirements (graded according to the National Cancer Institute Common Terminology Criteria for Adverse Events (NCI CTCAE) v4.03, Appendix G; see also Table 10):

- Thrombocytopenia Grades 3-4 with platelet count $<50,000/\text{mm}^3$: delay treatment with AM0010 and FOLFOX until platelet count returns to $\geq 100,000/\text{mm}^3$. Re-introduction of AM0010 should be administered at 80% and FOLFOX at dose level -1. If on a subsequent cycle these toxicities recur, AM0010 is reintroduced at 60% (-2 dose level) and FOLFOX at dose level -2 after the first recurrence. This will be accomplished by altering the dose schedule from 5 days on and 2 days off to 4 days on and 3 days off (80%), and 3 days on 4 days off (60%), respectively.
- Anemia Grades 3-4 with Hgb <8 g/dL: delay treatment with AM0010 and FOLFOX until Hgb returns to ≥ 10 g/dL. Re-introduction of AM0010 should occur at 80% and FOLFOX at dose level -1. If on a subsequent cycle these toxicities recur, AM0010 is reintroduced at 60% and FOLFOX at dose level -2 after the first recurrence.

Table 10: Hematologic Toxicity Dose Schedule Adjustment (Thrombocytopenia and Anemia Only)

| Occurrence of Hematologic TrAE* | FOLFOX Reintroduction | AM0010 Re-Introduction Dosing | Day 1 (FOLFOX Start) | Day 2 (FOLFOX End) | Day 3 | Day 4 | Day 5 | Day 6 | Day 7 |
|---------------------------------|-----------------------|-------------------------------|----------------------|--------------------|-------|-------|-------|-------|-------|
| – | Full dose | 100% | X | X | X | X | X | Rest | Rest |
| 1 st | –1 | 80% | X | X | X | X | Rest | Rest | Rest |
| 2 nd | –2 | 60% | X | X | X | Rest | Rest | Rest | Rest |

TrAE = Treatment-related Adverse Event; X = dosing

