- Neutropenia and neutropenic fever Grades 3–4 with ANC $<1,000/\text{mm}^3$: delay treatment with FOLFOX until ANC returns to $>1,000/\text{mm}^3$. Re-introduction of FOLFOX should occur at dose level –1. If on a subsequent cycle these toxicities recur, FOLFOX is reduced to dose level –2 after the first recurrence. AM0010 dosing will continue without interruption.

Non-Hematologic Toxicity Dose Schedule Adjustment Requirements (graded according to the NCI CTCAE v4.03, [Appendix G](#)):

- \geq Grade 3 fatigue, elevations in AST, ALT, alkaline phosphatase, or bilirubin require dose interruption and delay in subsequent therapy until recovered to \leq Grade 1 or pre-therapy baseline. Re-introduction of all agents at the previous dose level.
- \geq Grade 3 GI AEs such as diarrhea, nausea, vomiting, abdominal pain, and bloating require a delay in subsequent therapy until recovered to \leq Grade 1 or pre-therapy baseline. Re-introduction: Reduce offending agent by 1 dose level. Keep other agents unchanged.
- Other non-hematologic toxicities with an impact on organ function of \geq Grade 3 require dose reduction. Hold treatment for the offending agent (or all agents, see [Table 11](#)), delay in subsequent therapy until recovered to \leq Grade 1 or pre-therapy baseline. Re-introduction: Reduce offending agent by 1 dose level. Keep other agents unchanged.
If AM0010 is suspected to be one of the offending agents, reintroduction will be at the original dose after the first occurrence. If on a subsequent cycle these toxicities recur, the AM0010 treatment schedule will be decreased to 80%. Upon second recurrence of Grade 3 or 4 AE, the AM0010 dose will be decreased to 60%. This will be accomplished by altering the dose schedule from 5 days on and 2 days off to 4 days on and 3 days off (80%), and 3 days on 4 days off (60%), respectively. See below.
- It is common for oxaliplatin to cause Grade 3 or 4 neuropathy by 4 months of therapy. On both treatment arms following the dose modification in [Table 11](#) for neuropathy, if oxaliplatin needs to be discontinued, continue therapy with 5-FU/LV.

Table 11: Dose Interruption, Reduction, and Dose Schedule Modifications

| Adverse Event | Occurrence | Oxaliplatin | 5-Fluorouracil | AM0010 |
|---|-----------------|--|---|---|
| Hematological AEs | | | | |

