| Grades 3-4 Anemia or Grades 3-4 Thrombocytopenia | 1 st | Hold until G1 or baseline Reintroduce at dose level –1 | Hold until G1 or baseline Reintroduce at dose level –1 | Hold until G1 or baseline Reintroduce to Dose Level –1 |
| | 2 nd | Hold until G1 or baseline Reintroduce at dose level –2 | Hold until G1 or baseline Reintroduce at dose level –2 | Hold until G1 or baseline reintroduce to Dose Level –2 |
| | 3 rd | Hold until G1 or baseline No change in dose | Hold until G1 or baseline No change in dose | Hold until G1 or baseline No change in dose |
| Grades 3–4 neutropenia or Grades 3–4 leukopenia or Grades 3–4 neutropenic fever | 1 st | Hold until G1 or baseline Reintroduce at dose level –1 | Hold until G1 or baseline Reintroduce at dose level –1 | Continue dosing; no change in dose schedule |
| | 2 nd | Hold until G1 or baseline Reintroduce at dose level –2 | Hold until G1 or baseline Reintroduce at dose level –2 | |
| Hemolytic uremic syndrome (HUS) ² | 1 st | Discontinue | Hold until G1 or baseline No change in dose | Hold until G1 or baseline No change in dose |
| Non-hematological AEs | | | | |
| Grade 3 Diarrhea | | Hold until G1 or baseline No change in dose level | Hold until G1 or baseline Reintroduce at dose level –1 | Continue dosing; no change in dose schedule |
| Grade 4 Diarrhea | | Hold until G1 or baseline Reintroduce at dose level –1 | Hold until G1 or baseline Reintroduce at dose level –1 | |
| Cough ≥Grade 3 Dyspnea ≥Grade 3 Hypoxia ≥Grade 3 Pneumonitis ≥Grade 3 | | Hold oxaliplatin until interstitial lung disease is ruled out. If interstitial lung disease, discontinue oxaliplatin. | Hold until G1 or baseline No change in dose | Hold until G1 or baseline No change in dose schedule |
| Grade 3 Fatigue | | Hold until G1 or baseline No change in dose level | Hold until G1 or baseline No change in dose level | Hold until G1 or baseline No change in dose schedule |

Table 11: Dose Interruption, Reduction, and Dose Schedule Modifications

| Adverse Event | Occurrence | Oxaliplatin | 5-Fluorouracil | AM0010 |
|--|------------|--|-------------------|---|
| Non-hematological AEs | | | | |
| Other G3/G4 non-hematological AEs ^{3,4} | | Hold until G1 or baseline Reduce offending agent by 1 dose level ¹ | | No change in dose schedule |
| Hypomagnesemia | | Hold until G1 or baseline No change in dose level | | |
| Neurological AEs | | | | |

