5.2.1 FOLFOX

Recommended dose reduction for the components of FOLFOX is described in [Table 12](#) and is based on the AE table described in [Table 11](#) and [Appendix D](#). Leucovorin doses may be adjusted per institutional guidelines in the event of a supply shortage.

Table 12: Dose Reduction Levels^a for FOLFOX

| Drug | Dose Level | | |
|---|------------------------|------------------------|------------------------|
| | Starting Dose | -1 | -2 ^b |
| Oxaliplatin | 85 mg/m ² | 65 mg/m ² | 50 mg/m ² |
| 5-FU bolus | 400 mg/m ² | Omit | Omit |
| 5-FU continuous infusion over 46–48 hours | 2400 mg/m ² | 1900 mg/m ² | 1500 mg/m ² |
| dl-Leucovorin/l-Leucovorin ^c | 400 mg/m ² | 100% | 100% |

^aIf an AE is believed likely to be due to 1 drug, it is permissible to decrease dose of that drug only.

^bFurther dose levels (-3, -4, etc.) will be 20% dose reductions from the previous level for oxaliplatin and 5-FU continuous infusion. In addition, the bolus dose of 5-FU will continue to be omitted and the leucovorin dose will remain unadjusted (100%).

^cDosing of leucovorin will remain fixed at 100% of the recommended dose. Non-racemic L-leucovorin dose is 200 mg/m².

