5.2.2 AM0010 and FOLFOX Dose Modifications

If a patient experiences any of the following treatment-related toxicities, dosing will be postponed until the toxicity has resolved to Grades 0–1 (as defined by NCI CTCAE v4.03) or returns to the patient's baseline value. Re-initiation of therapy may occur during a cycle of therapy or at the beginning of the next cycle of dosing. Dose reductions for AM0010 plus FOLFOX are shown [Table 13](#).

Table 13: Dose Reduction Levels for AM0010 plus^a FOLFOX

| FOLFOX | Dose Level | | | |
|---|---------------------------------|--------------------------------|--------------------------------|------------------------|
| | Starting Dose | -1 | -2 ^b | |
| Oxaliplatin | 85 mg/m ² | 65 mg/m ² | 50 mg/m ² | 50 mg/m ² |
| 5-FU bolus | 400 mg/m ² | Omit | Omit | Omit |
| 5-FU continuous infusion over 46–48 hours | 2400 mg/m ² | 1900 mg/m ² | 1500 mg/m ² | 1500 mg/m ² |
| dl-Leucovorin/l-Leucovorin ^c | 400 mg/m ² | 100% | 100% | 100% |
| AM0010 | Dose Level | | | |
| | Starting Dose | -1 | -2 | |
| | 100% (5 days on and 2 days off) | 80% (4 days on and 3 days off) | 60% (3 days on and 4 days off) | |

^aIf an AE is believed likely to be due to 1 drug, it is permissible to decrease dose of that drug only.

^bFurther dose levels (-3, -4, etc.) will be 20% dose reductions from the previous level for oxaliplatin and 5-FU continuous infusion. In addition, the bolus dose of 5-FU will continue to be omitted, and the leucovorin dose will remain unadjusted (100%).

^cDosing of leucovorin will remain fixed at 100% of the recommended dose. Non-racemic L-leucovorin dose is 200 mg/m².

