5.3 Study Treatment Dose Delays

Patients who do not meet the minimum re-treatment criteria on Day 14 (± 3 days) of the cycle and do not meet the criteria for discontinuation will delay treatment and be followed for resolution of toxicity to levels specified in the package insert for resuming FOLFOX. Cycles may also be delayed for logistic or personal reasons, but patients who have not received therapy for 28 days from the scheduled start of cycle should be discontinued from AM0010 and/or FOLFOX treatment unless:

1. The patient is clinically benefiting from therapy, defined as radiographic or symptomatic improvement in the opinion of the Investigator, and
2. Approval is obtained from Lilly or Lilly's designee Medical Monitor in collaboration with the Investigator. Study treatment should be discontinued for any dose delay greater than eight weeks (>56 days).

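### After Grade 3–4 neutropenia, Protocol Section 5.2 restarts FOLFOX at ANC above 1,000/mm³, while Table 11 and Appendix D hold it until Grade 1 or baseline

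*Protocol*

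**What the plan says.** The Protocol states restart conditions after hematologic toxicity in several places.

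- **Section 5.2, neutropenia bullet.** The trigger is Grade 3–4 with ANC below 1,000/mm³. The instruction is to "delay treatment with FOLFOX until ANC returns to" more than 1,000/mm³, then resume at dose level −1 (level −2 after a recurrence). AM0010 continues throughout.
- **Table 11 and Appendix D, neutropenia row.** For both oxaliplatin and 5-FU the entry reads "Hold until G1 or baseline Reintroduce at dose level" −1, and −2 at the second occurrence. AM0010 continues.
- **Section 5.2, anemia and thrombocytopenia bullets.** For anemia, sites are to "delay treatment with AM0010 and FOLFOX until Hgb returns to" at least 10 g/dL. For thrombocytopenia the level is a platelet count of at least 100,000/mm³. Neither bullet mentions baseline. Table 11 and Appendix D give Grade 1 or baseline for both.
- **Section 5.2.2 (AM0010 plus FOLFOX).** The general rule is that "dosing will be postponed until the toxicity has resolved to Grades" 0–1, or has returned to the patient's baseline.
- **Section 5.3.** Patients who miss the re-treatment criteria at the end of a cycle "will delay treatment and be followed for resolution of toxicity to levels specified in the package insert for resuming FOLFOX".
- **Section 3.1.1, item 10.** Entry requires ANC of at least 1.5 × 10⁹/L, platelets of at least 100 × 10⁹/L, and "Hemoglobin ≥ 9.0 g/dL".

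**The concern.** The bullet and the tables cover the same toxicity and the same drugs, and both are current text. The Section 5.2 bullets appear under a heading that calls them requirements, so they cannot be read as loose guidance beside a binding table. If the two conditions differ, re-treatment with myelosuppressive chemotherapy after Grade 3–4 neutropenia depends on which page the site reads. A site can comply with one instruction and breach the other on the same day.

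What is at stake is patient safety and consistent dosing in both arms. The analyses touched are the dose-delay and dose-intensity summaries in SAP 10.1.3 and 10.1.1, which are descriptive.

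**Working it through.** The Protocol gives no calculated figure to reproduce. The check sets the restart rules side by side and uses the entry criteria to bound baseline.

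| Toxicity | Section 5.2 bullet | Table 11 and Appendix D |
|---|---|---|
| Neutropenia (FOLFOX) | ANC > 1,000/mm³ | Grade 1 or baseline |
| Anemia (AM0010 and FOLFOX) | Hgb ≥ 10 g/dL | Grade 1 or baseline |
| Thrombocytopenia (AM0010 and FOLFOX) | platelets ≥ 100,000/mm³ | Grade 1 or baseline |

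**Neutropenia.** Let L be the lower ANC limit of Grade 1 and B the patient's baseline. The text allows restart above 1,000. The tables allow it at the lower of L and B.

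1. *Grade.* The bullet places Grades 3–4 below 1,000. A count just above 1,000 has left Grade 3 and entered Grade 2. It is not Grade 1, so L exceeds 1,000. This needs no printed grade table.
2. *Baseline.* 1.5 × 10⁹/L equals 1,500/mm³. A patient whose baseline is at or above the entry minimum is not back at baseline just above 1,000.
3. *Size.* The disputed range is min(L, B) − 1,000. With B = 1,500 it is at most 1,500 − 1,000 = 500/mm³, and smaller if L is below 1,500. Appendix G only links to CTCAE v4.03, so L is not printed. If L is assumed to be 1,500, the range is 500/mm³ for every patient with B of 1,500 or more.

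**Anemia.** Let F be the Grade 1 hemoglobin floor, also unprinted. The text exceeds the tables by 10 − min(F, B).

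- Assuming F = 10: B = 9.0 gives 1.0 g/dL, B = 9.2 gives 0.8 g/dL, and B of 10 or more gives 0. The text is the stricter rule wherever B is below 10.
- If F is below 10, patients with B of 10 or more are affected too, and the gap can exceed 1.0 g/dL.
- If F is above 10, the text is the looser rule for patients with B above 10.

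**Thrombocytopenia.** The restart count equals the entry minimum (100 × 10⁹/L = 100,000/mm³). The missing baseline alternative therefore matters only if a patient's count fell below 100,000 between eligibility testing and first dose, or if the Grade 1 platelet floor is below 100,000. The documents do not print that floor.

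**Precedence.** Section 5.2.1 says "Recommended dose reduction for the components of FOLFOX is described in" Table 12 and rests on Table 11 and Appendix D, but this concerns how far to reduce, not when to restart. Section 5.2.2 agrees with the tables, as do Section 5.2's own non-hematologic bullets for fatigue, liver tests and gastrointestinal events. The three hematologic bullets are the outliers.

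**The case against.** The best defense is that little harm follows. A site that waits for the stricter condition breaches neither rule. Text and tables agree on what is restarted: level −1 drops the 5-FU bolus and cuts oxaliplatin from 85 to 65 mg/m² and infusional 5-FU from 2400 to 1900 mg/m². Section 5.1.2 requires review of hematology before and during chemotherapy, and it points to regional prescribing information and institutional practice for an established backbone.

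These mitigations stand, and they keep the point below a critical one. They do not resolve it. Nothing tells a site to take the stricter rule, and a reduced dose does not settle the day on which it may be given.

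A second objection concerns Section 5.3. A reader might infer that its package-insert reference is a third conflicting standard. The documents do not support that. The insert levels are not reproduced and could match either rule, and the section is a general cycle-delay provision. It is a reference left unreconciled with the other rules.

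A third is that the anemia text errs on the cautious side. Under the assumed floor of 10 g/dL it does, but longer holds have a cost. Section 5.3 says that patients untreated for 28 days from the scheduled cycle start should be discontinued from AM0010 and/or FOLFOX, unless they are benefiting and the medical monitor approves. Table 4 reports treatment-related Grade 3 anemia in 11 of 25 pancreatic patients (44%) on FOLFOX with AM0010 5 µg/kg. That is Phase 1 experience, not a rate for this trial's 5-on/2-off schedule, and how many of those patients had a baseline below 10 is unknown.

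**Conclusion.** The neutropenia rule is wrong as written and should be fixed. The contradiction rests on the bullet's own trigger and on a baseline no lower than the entry minimum. Eligibility labs may be up to 21 days before randomization, and treatment may start up to 3 days after it, so an occasional patient could have a lower pre-dose count and a narrower disputed range.

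The anemia and platelet omissions are secondary. A reader might conclude that the anemia mismatch touches only patients who enter with hemoglobin of 9.0 to below 10 g/dL, never exceeds 1.0 g/dL, and vanishes for entry at 10 or above. The documents do not establish those limits. They require the unprinted Grade 1 floor to be 10 g/dL and the entry value to be the baseline, whereas SAP 7.2 takes the last value on or before first dose as the safety baseline. What can be said is conditional: with a floor of 10, the omission matters for patients whose pre-dose baseline is below 10, which the entry criterion permits.

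No patient count can be given, because the documents contain neither a neutropenia rate nor a baseline hemoglobin distribution. There is no effect on alpha, sample size or the primary overall survival test.

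**What to change.** 1. In Section 5.2, change the neutropenia restart criterion to Grade 0–1 or the patient's baseline, to match Table 11 and Appendix D.
2. Use one restart wording for anemia and for thrombocytopenia across the Section 5.2 bullets, Table 11, Appendix D and Section 5.2.2. The sponsor's clinicians should decide whether the baseline alternative applies, because adopting it for anemia would relax what appears to be the stricter rule.
3. In Section 5.3, state that the package-insert levels apply in addition where they are stricter.

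The cost is a short protocol amendment. Under Section 11.2 it needs IRB/IEC approval before use, unless it is needed for patient safety. There is no statistical cost. Patients already treated may have been handled under either rule, so the dose-delay and dose-intensity summaries should note the date of the change.

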6.3 ARM 1 Subsequent Cycles AFTER Discontinuation of FOLFOX

6.3.1 ARM 1 (Investigational) Maintenance Cycles after Termination of FOLFOX (Every 28 Days)

In the absence of tumor progression, after completion of up to 12 planned cycles of FOLFOX or discontinuation of FOLFOX due to toxicity, patients assigned to ARM 1 may continue on AM0010 monotherapy at 10 µg/kg (either 0.8 mg for patients weighing ≤80 kg or 1.6 mg for patients weighing >80 kg, administered 5 days on and 2 days off).

Dose reductions in maintenance are the same as in combination at 80% and 60% by altering dose schedule. The 80% dose is administered 4 days on and 3 days off and the 60% dose is administered 3 days on and 4 days off.

The numbering of cycles during maintenance treatment in ARM 1 will follow the convention of “Maintenance Cycles” with Maintenance C1D1 beginning after discontinuation of FOLFOX and start of monotherapy AM0010 as described above. Each Maintenance Cycle will be 28 days/4 weeks in duration.

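### For recurrent organ-affecting non-hematologic toxicity with AM0010 suspected, the Section 5.2 text steps AM0010 down to 80% and then 60%, but Table 11 and Appendix D print no change and no recurrence step

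*Protocol*

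**What the plan says.** The non-hematologic part of Protocol Section 5.2 is headed as requirements. Its third bullet covers "Other non-hematologic toxicities with an impact on organ function of" Grade 3 or higher. Where AM0010 is thought to be one of the causes, it restarts at the original dose after the first occurrence. After that, "If on a subsequent cycle these toxicities recur, the AM0010 treatment schedule will be decreased to 80" percent. Next, "Upon second recurrence of Grade 3 or 4 AE, the AM0010 dose will be decreased to 60" percent. The mechanism is stated too: "This will be accomplished by altering the dose schedule from 5 days on and 2 days off", to 4 on/3 off for 80% and 3 on/4 off for 60%.

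Table 11, in the same section, has one row for other Grade 3/4 non-hematologic events. Its Occurrence cell is blank. The hold and the one-level reduction of the offending agent are printed under oxaliplatin and 5-FU, and the AM0010 cell reads "no change in dose schedule". Appendix D has the same AM0010 entry, again without an occurrence step. The row for cough, dyspnea, hypoxia and pneumonitis gives AM0010 "Hold until G1 or baseline No change in dose schedule" and has no occurrence step.

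Table 13 (Section 5.2.2) defines the reduced AM0010 levels, for example "80% (4 days on and 3 days off"), but links them to no event row. Section 6.3.1 adds: "Dose reductions in maintenance are the same as in combination at 80% and 60% by altering dose schedule".

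**The concern.** AM0010 is reduced only by taking away dosing days, so an instruction not to change the schedule is an instruction not to reduce. For the same patient with the same repeated event, the text requires a step down and the table cell requires none. The bullet itself sends the reader to Table 11, so a site that follows the cross-reference arrives at the conflicting entry.

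The patients concerned have had Grade 3 or higher organ toxicity at least twice, with the investigational drug suspected, and they inject it at home. The trial plans about 150 sites. What is at stake is patient safety and uniform dosing in Arm 1. AM0010 relative dose intensity, which the SAP summarizes in Section 10.1.1, would also partly reflect which instruction a site happened to follow.

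**Working it through.** **1. The protocol's own percentages.** The full schedule is 5 dosing days per week. 4/5 = 0.80 and 3/5 = 0.60, so the stated 80% and 60% are reproduced and match Table 13.

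**2. Full dose per combination cycle.** Fixed doses are 0.4 mg (≤80 kg) and 0.8 mg (>80 kg), from Section 5.1.1. Doses per 14 days = 2 × 5 = 10. Then 10 × 0.4 = 4.0 mg and 10 × 0.8 = 8.0 mg, which agrees with the planned dose intensity in SAP Table JZGB.10.1.

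**3. Text against table, event by event (AM0010 suspected).**

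| Event | Section 5.2 text | Other row, Table 11 and Appendix D |
|---|---|---|
| First occurrence | restart at 100% | no change (100%) |
| First recurrence | 80% | no change (100%) |
| Second recurrence | 60% | no change (100%) |

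The restart dose agrees in the first line and differs in the next two.

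**4. Size per 14-day combination cycle.** Doses = 2 × dosing days per week.

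| | Text | Table | Table ÷ text |
|---|---|---|---|
| First recurrence | 8 doses: 3.2 mg (≤80 kg), 6.4 mg (>80 kg) | 10 doses: 4.0 mg, 8.0 mg | 10/8 = 1.25 |
| Second recurrence | 6 doses: 2.4 mg, 4.8 mg | 10 doses: 4.0 mg, 8.0 mg | 10/6 = 1.67 |

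**5. Size per 28-day maintenance cycle.** Doses = 4 × dosing days per week: 16 and then 12 under the text, 20 under the table. The ratios are the same. The milligrams depend on a dose that the protocol prints in two ways:

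| Maintenance dose (≤80 / >80 kg) | Where printed | First recurrence, text vs table | Second recurrence, text vs table |
|---|---|---|---|
| 0.8 / 1.6 mg | Body text of the Synopsis and Sections 2.2, 5.1.1 and 6.3.1; SAP Sections 6.3 and 10.1.1 | 12.8 vs 16.0 mg; 25.6 vs 32.0 mg | 9.6 vs 16.0 mg; 19.2 vs 32.0 mg |
| 0.4 / 0.8 mg | Notes beside the Arm 1 diagrams in the Synopsis and Sections 2.2 and 5.1.3 | 6.4 vs 8.0 mg; 12.8 vs 16.0 mg | 4.8 vs 8.0 mg; 9.6 vs 16.0 mg |

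**6. Is the table only silent?** The anemia/thrombocytopenia row prints first, second and third steps, and the neutropenia row prints first and second. The tables therefore show recurrence steps where they are meant to apply. In the Other row the AM0010 cell carries a positive instruction.

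**7. Does anything else settle it?**
- Table 11 note 1 allows a reduction of one drug alone when that drug is the likely cause. It is permissive and gives no levels; the text is mandatory and applies when AM0010 is one of several suspects.
- The opening of 5.2 ties investigator judgment to the guidelines that follow it, which are the ones in conflict.
- The Synopsis allows the drugs that are not responsible to continue. It does not set the level of the one that is.
- Section 5.2.2 postpones dosing until Grade 0–1 or baseline and points to Table 13, but does not say which event triggers which level.
- Section 6.3.1 confirms the levels for maintenance, not the trigger.
- No rule was found that ranks text above table or the reverse.

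**The case against.** The best defense is that the two sources can be read together. The text is headed as requirements, is conditional on AM0010 being suspected, and is worded as mandatory. The table cell carries no condition and can be taken as the default when AM0010 is not suspected. On that reading the table lacks only a footnote. This is a sensible reconstruction and probably the intent, but the table does not say it, and a site working from Appendix D alone would not see the condition.

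It is also fair that a reader might infer that patients would be held on full dose with no protection. The documents do not support that. Section 4.1 allows AM0010 to be discontinued for adverse events or by investigator decision in consultation with the Medical Monitor, the Synopsis names unacceptable toxicity as an end to treatment, and Section 5.2.2 postpones dosing until recovery. These limit the harm. They do not tell the site what level to restart at after a recurrence.

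Two neighboring items might look like further contradictions. For diarrhea, the gastrointestinal bullet neither names nor exempts AM0010, while the table continues it. For liver tests, the tables have no row, but the 5.2 text gives an explicit rule. Both are ambiguities at most.

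The tables were read from PDF and merged cells may have been flattened. The AM0010 entry for the Other row is the same in Table 11 and Appendix D, so a reading error is unlikely.

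**Conclusion.** The inconsistency is real and confined. It applies to other non-hematologic toxicity of Grade 3 or higher with an impact on organ function, with AM0010 suspected, from the first recurrence on. A site following the Other row as printed gives 10 doses per 14 days where the text requires 8 and then 6, which is 25% and then 67% more drug. The maintenance counts are 20 against 16 and then 12 per 28 days; those milligrams rest on which printed maintenance dose is used, so both are shown. For the pulmonary row the same gap follows if those events fall under the text's Other bullet, as the order of the bullets suggests.

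The documents do not say how often such events occur or recur, so no overall excess exposure can be stated. A reader might also infer a threat to the primary result. The documents give no basis for that: the overall survival test, alpha, power and sample size do not depend on this rule. The point should be fixed for patient safety and consistent dosing.

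**What to change.** In Table 11 and Appendix D, in both the Other and the pulmonary rows, add AM0010 steps for when AM0010 is suspected:
- 1st occurrence: hold until Grade 1 or baseline, restart at the original dose.
- 2nd occurrence: restart at 80% (4 on/3 off).
- 3rd occurrence: restart at 60% (3 on/4 off).

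Limit the no-change entry to cases where AM0010 is not suspected, and note that the same steps apply in maintenance. A short site letter ahead of the amendment could cover this recurrence step alone.

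Optional and minor: state one AM0010 instruction for Grade 3 and Grade 4 diarrhea in both text and tables, and add a liver-test row that repeats the 5.2 rule.

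The cost is amendment wording in two tables, plus the letter if used. Alpha, power and sample size do not change.
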